8.1.4.1.5 Imputation Methods

The following methods will be used for missing data imputation:

Observed Cases (OC): The OC analysis will not impute values for missing evaluations, and thus a subject who does not have an evaluation on a scheduled visit will be excluded from the OC analysis for that visit.

Multiple Imputation (MI): The MI analysis imputes missing data multiple times under appropriate random variation and thus generates multiple imputed "pseudo-complete" datasets. Results will be aggregated across the multiple imputed datasets, overcoming drawbacks of the single imputation methods.

Non-Responder Imputation (NRI): NRI applies to binary endpoints only. In NRI analysis, subjects who prematurely discontinue study drug will be considered non-responders after discontinuation.

The NRI approach will serve as the primary analysis approach for key binary endpoints. The MI approach will serve as the primary analysis approach for key continuous endpoints. Sensitivity analyses based on OC will also be conducted for key endpoints.

8.1.4.2 Long-Term Efficacy Analysis for Period 1 and Period 2 Combined

The efficacy endpoints of long-term efficacy analysis are listed in Section [5.3.3.2](#) and will be summarized for all visits.

Long-term efficacy by time point will be summarized using descriptive statistics. For binary endpoints, frequencies and percentages will be summarized. For continuous endpoints, the mean and standard deviation will be reported.

8.1.5 Safety Analyses

8.1.5.1 General Considerations

Safety analyses will be carried out using the Safety Analysis Set. Analyses will be conducted for Period 1 alone, as well as for Period 1 and Period 2 combined.

Safety analyses are based on treatments actually received. Safety will be assessed by AEs, physical examination, laboratory assessments, ECG, and vital signs. Frequency tables and lists of subjects with treatment-emergent AEs by preferred term as in the Medical Dictionary for Regulatory Activities (MedDRA) dictionary, by system organ class, by severity, and by relationship to the study drug as assessed by the Investigator will be provided. The changes from baseline in vital signs, physical examination results, and clinical laboratory values will be analyzed in a descriptive manner. Shift of laboratory values from baseline to defined time points will be tabulated.

Missing safety data will not be imputed.

8.1.5.2 Analysis of Adverse Events

Unless otherwise specified, the following conventions apply for both the Period 1 safety analysis and the combined safety analysis of Period 1 and Period 2.

8.1.5.2.1 Treatment-Emergent Adverse Events (TEAE)

AEs will be coded using MedDRA. A TEAE is defined as AE that began or worsened in severity after initiation of study drug.

AEs starting more than 30 days following the last dose of study drug will not be included in summaries of TEAEs. For subjects who continued into Period 2, AEs that are reported in Period 2 will be captured in the combined safety analysis of Period 1 and Period 2.

As a general safety summary, the number and percentage of subjects experiencing TEAEs will be summarized for each treatment group for the following AE categories:

- All AEs;
- All severe AEs;
- All reasonably possibly related AEs;
- All SAEs;
- Frequent AEs (reported in 2% of subjects or more in any treatment group);
- Frequent reasonably possibly related AEs (reported in 2% of subjects or more in any treatment group);
- Discontinuations due to AEs;
- Death.

Additional AEs may be considered for tabulation/summary based on recommendations from Clinical and Safety as deemed appropriate.

TEAEs will be summarized and presented by system organ classes (SOCs) and preferred terms (PTs) using MedDRA. The SOCs will be presented in alphabetical order, and the PTs will be presented in alphabetical order within each SOC.

TEAE will also be summarized by maximum severity and by maximum relationship.

The AEs of special interest (including but not limited to serious infection, opportunistic infection, herpes zoster, TB, gastrointestinal perforations, malignancies, MACE, renal dysfunction, anemia, increased CPK, non-cardiac, non-CNS embolic and thrombotic events, and drug-related hepatic disorders) will be summarized. Event rate (per 100 patient years) for AEs of special interest will also be summarized for the combined safety analysis of Period 1 and Period 2.

All AEs leading to discontinuation of study drug will be presented in listing format. A listing by treatment group of TEAEs grouped by SOC and MedDRA preferred term with subject identification numbers will be generated.

8.1.5.2 Serious Adverse Events and Death

All treatment-emergent SAEs and AEs leading to death will also be presented in listing format. In addition, SAEs will be summarized by SOC and MedDRA PT.

8.1.5.3 Analysis of Laboratory, Vital Sign, and ECG Data

Changes from baseline by visit, and changes from baseline to minimum value, maximum value, and final values in continuous laboratory data, and vital signs will be summarized by treatment group.

Baseline values are defined as the last non-missing measurements recorded on or before the date of the first dose of study drug in Period 1.

The laboratory data will be categorized as Grade 1, Grade 2, Grade 3, and Grade 4 according to OMERACT criteria (Rheumatology Common Toxicity Criteria v.2.0). For creatine phosphokinase and serum creatinine, NCI CTC criteria will be used. The shift tables will tabulate the number and percentage of subjects with baseline and post-baseline values by grade level.

Listings will be provided for potentially clinically significant laboratory values and vital signs.

8.1.6 Pharmacokinetic and Exposure-Response Analyses

Individual upadacitinib plasma concentrations at each study visit will be tabulated and summarized with appropriate statistical methods.

Data from this study may be combined with data from other studies for the population PK and exposure-response analyses. Population PK and exposure-response analyses of only data from this study may not be conducted. The following general methodology will be used for the population PK and exposure-response analyses.

Population PK analyses will be performed using the actual sampling time relative to dosing. PK models will be built using a non-linear mixed-effects modeling approach with

NONMEM software (Version 7, or a higher version). The structure of the starting PK model will be based on the PK analysis of data from previous studies. The CL/F and V/F of upadacitinib will be the PK parameters of major interest in the analyses. If necessary, other parameters, including the parameters describing absorption characteristics, may be fixed if useful in the analysis.

The evaluation criteria described below will be used to examine the performance of different models.

1. The objective function of the best model is significantly smaller than the alternative model(s).
2. The observed and predicted concentrations from the preferred model are more randomly distributed across the line of unity (a straight line with zero intercept and a slope of one) than the alternative model(s).
3. Visual inspection of model fits, standard errors of model parameters and change in inter-subject and intra-subject error.

Once an appropriate base PK model (including inter- and intra-subject error structure) is developed, empirical Bayesian estimates of individual model parameters will be calculated by the posterior conditional estimation technique using non-linear mixed-effects modeling. The relationship between these conditional estimates CL/F and V/F values with only potentially physiologically relevant or clinically meaningful covariates (such as subject age, sex, body weight, concomitant medications, laboratory markers of hepatic or renal function, etc.) will be explored using stepwise forward selection method, or another suitable regression/smoothing method at a significance level of 0.05. After identification of all relevant covariates, a stepwise backward elimination of covariates from the full model will be employed to evaluate the significance (at $P < 0.005$, corresponding to a decrease in objective function > 7.88 for one degree of freedom) of each covariate in the full model.

Linear or non-linear relationships of primary PK parameters with various covariates will be explored.

Relationships between upadacitinib exposure and clinical observations (primary efficacy variable) will be explored. Exposure-response relationships for secondary efficacy variables and/or some safety measures of interest may also be explored. The relationship between exposure (e.g., population PK model predicted average concentrations, area under the curve, trough concentrations, the individual model-predicted PK profiles, or some other appropriate measure of exposure) and drug effect will be explored. Several classes of models (e.g., linear, log-linear, exponential, E_{max} , sigmoid E_{max} , etc.) will be evaluated to characterize the exposure-response relationship based on observed data. Results of the PK and exposure-response analyses may be summarized in a separate report prior to regulatory filing of upadacitinib for the treatment of RA, rather than in the CSR.

Additional analyses will be performed if useful and appropriate.

8.1.7 Statistical Analysis of Biomarker Data

Summary statistics for the in vivo pharmacodynamic biomarkers (including but not limited to NK, NKT, B cells, and T cells) at baseline and post-treatment time points (Weeks 8 and 12/PD in Period 1, and Weeks 16, 24, 36, 48 and every 24 weeks thereafter in Period 2), in addition to change from baseline at each time will be provided; this will include mean, standard deviation, median, quartiles, and range for each group. The pharmacodynamic effect of each biomarker between the placebo and upadacitinib treatment groups will be evaluated via a non-linear mixed-effects modeling approach with Change from baseline of the biomarker as response variable, Treatment, Time, and Treatment \times Time interaction as fixed-effects, the corresponding baseline biomarker score as a covariate, and "subjects nested within the treatment group" as a random-effect. Other baseline variables such as age, weight, etc., may be considered as appropriate. For biomarkers identified to have significant overall treatment effect via the non-linear mixed-effects modeling analysis, dose-response models with the biomarker as a continuous response will be explored. In addition to the above analyses of biomarkers

individually, the effect of certain combination of biomarkers on the treatment groups may be explored.

If the optional exploratory research variables including an additional panel of prognostic, predictive, and pharmacodynamic biomarkers are evaluated, then those data may be analyzed as follows. The association of biomarkers to the efficacy and safety endpoints may be explored for each biomarker one at a time, and also for combinations of biomarkers via some multivariate predictive modeling algorithms. Optimal multivariate combinations of biomarkers that associate with efficacy endpoints, subject response/non-response (with respect to appropriate clinical endpoints), and also with safety endpoints may be explored via a variety of statistical predictive modeling algorithms. Also cut-points for individual biomarkers and optimal combinations of biomarkers that differentiate the subject response with respect to efficacy/safety endpoints may be explored. The significance of these multivariate combinations of biomarkers may be assessed via at least 20 iterations of 5 fold cross-validation.

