5.3.6.2 Exploratory Research Variables and Validation Studies

Optional samples may be collected to conduct exploratory investigations into known and novel biomarkers. The types of biomarkers to be analyzed may include, but are not limited to nucleic acids, proteins, lipids, or metabolites.

Biomarker assessments may be used to assess and generate prognostic, predictive, pharmacodynamic, or surrogate biomarker signatures. These assessments may be explored in the context of RA or related conditions and/or upadacitinib or drugs of similar classes. The results from these analyses are exploratory in nature and may not be included with the clinical study report (CSR).

The samples may also be used to develop new therapies, research methods or technologies. In addition, samples from this study may be stored for future use. Samples may then be used to validate putative biomarker signatures obtained from a prospective study, leading to the development of diagnostic tests.

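### Repeated cross-validation is named as the way to assess the significance of biomarker combinations, but it supplies no null distribution, so the false-positive rate is undefined

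*Protocol*

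**What the plan says.** The last paragraph of Protocol Section 8.1.7 covers the optional exploratory panel and applies only if that panel is evaluated. It describes three steps, all permissive.

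- Search: optimal multivariate combinations associated with efficacy, response or safety "may be explored via a variety of statistical predictive modeling algorithms".
- Cut-points: "Also cut-points for individual biomarkers and optimal combinations of biomarkers that differentiate the subject response with respect to efficacy/safety endpoints may be explored".
- Assessment: "The significance of these multivariate combinations of biomarkers may be assessed via at least 20 iterations of 5 fold cross-validation".

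The section gives no performance measure, null hypothesis, test statistic, p-value rule or level for the third step. It does not say whether the search and cut-point steps are repeated inside each training fold.

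On status, Protocol Section 5.3.6.2 calls the results exploratory and allows them to be left out of the clinical study report. SAP Section 3.0 sends biomarker analyses to a separate document, which was not available for this review.

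**The concern.** A significance statement needs a reference: how the chosen statistic behaves when the markers carry no information about the outcome. Repeating 5-fold cross-validation re-divides the same subjects, with their true outcomes attached. The spread across repeats is splitting noise around one fixed data set. More repeats shrink that noise but add no subjects and no information about the null.

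The order of the text raises a second question. Optimal combinations and cut-points come first, and then these combinations are assessed. If selection has already used every subject, the held-out folds are no longer independent of it.

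At stake is how a chance signature gets filtered. Protocol Section 12.0 lets aggregate exploratory results be published or presented. Section 5.3.6.2 foresees signatures being validated, "leading to the development of diagnostic tests". Section 5.3.1.2.2 allows samples to be kept for up to 20 years after study completion, so this work may still lie ahead.

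**Working it through.** **Plan's own figure.** There is none to reproduce. Section 8.1.7 attaches no error rate to this step. The 0.025 per dose in Protocol Section 8.1.4.1.4 covers only the primary and ranked key secondary endpoints.

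**Inputs from the documents.** 20 or more iterations of 5 folds, so at least 20 × 5 = 100 held-out folds, each subject being held out once per iteration. The total sample size is 600; the number consenting to optional samples is not given.

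**Assumptions.** No marker is related to outcome; independent normal markers; n = 200 or 400; 20 or 100 candidates; best 5 combined; a binary outcome; 20 × 5-fold cross-validation scored by AUC (area under the ROC curve); nominal level 5%. Cut-point search, multiple algorithms and multiple endpoints were not simulated.

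- Set A: 60% response, ridge score, two-sided tests, 300 data sets in each of four settings.
- Set B: balanced outcome, correlation-weighted score, one-sided tests, 1,000 data sets in each of three settings (n/markers 200/20, 400/20, 400/100), plus 400 data sets at 200/20.

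**Rules compared.**

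- Naive t over iterations: t = (mean AUC − 0.5) / (SD of the 20 AUCs / √20). The denominator holds only splitting noise, so t grows with the number of iterations.
- Rank test per iteration: z = (AUC − 0.5) / √[(n + 1)/(12·n1·n0)]. With n = 200 and n1 = n0 = 100 the denominator is √(201/120,000) = 0.041. It is approximate here, because pooled held-out scores come from five fits that share subjects.
- Corrected resampled t over the 100 folds: the factor √(1/100) = 0.10 becomes √(1/100 + 1/4) = 0.51.

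**False-positive rates under the null.**

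| Rule | Set A | Set B |
|---|---|---|
| Nested selection, naive t over 20 iterations, in the signature's favour | 34–38% | 37–42% |
| Nested, naive t over 100 folds | – | 38–42% |
| Nested, 2.5th percentile of the 20 AUCs above 0.5 | – | 14–16% |
| Nested, rank test on averaged held-out predictions | – | 12–18% |
| Nested, corrected resampled t | – | 10–12% |
| Nested, median of 20 p-values | 10–11% | 9–12% |
| Nested, twice that median | – | 4.5–5.7% |
| Nested, at least 19 of 20 iterations with p ≤ 0.05 | – | 1.4–1.8% |
| Nested, all 20 iterations | – | 0.6–0.8% |
| Nested, median of the 100 fold p-values | – | 0.1–0.3% |
| Selection on all data before the folds, median p | 65–100% | 77–100% |

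A further null simulation gave 34–38% for the naive t in the signature's favour, 7–9% for the one-sided median p with nested selection, and 82–100% with selection before the folds.

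**Bias of the estimate.** With nested selection the mean null AUC in Set B was 0.496–0.498. The performance estimate is not inflated; the trouble lies in turning it into a significance claim.

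**After the fix.** Shuffling outcomes 99 times and repeating selection plus the whole cross-validation gave 5.5% false positives in 400 null data sets (n = 200, 20 markers). The Monte Carlo standard error is √(0.055 × 0.945/400) = 1.1 points, so this is consistent with 5%. The simulated data had no treatment arms, so the shuffle was unrestricted.

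**The case against.** A reader might infer that unrelated combinations would be declared significant far more than 5% of the time. The documents do not support that. Section 8.1.7 fixes no level, statistic or decision rule, so no error rate follows from it. Several rules built on the same 20 × 5-fold scheme hold about 5% or fall well below it. Nor does the text commit to selecting before splitting: it is silent, and silence is not leakage. A permutation reference is not excluded either, and the details may sit in the separate biomarker document.

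The two-sided naive t in Set A rejects in 74–80% of runs, but that is not a rate of false signatures. Only 34–38% of runs favour the signature; the other rejections point to worse-than-chance prediction, which nobody would report as a finding.

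The consequences are also limited. Everything is optional. The diagnostic-test sentence in Section 5.3.6.2 describes using stored samples to validate putative signatures, so validation comes before any test. Section 12.0 states that the results are not fit for clinical decisions.

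Finally, one permutation scheme does not suit prognostic, predictive and pharmacodynamic claims alike, and a change of wording alone would remove the misstatement.

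All of this stands and limits the point. It does not answer the core: the only method statement available names cross-validation as the means of assessing significance, and cross-validation alone cannot do that. Detail at this level is not foreign to the protocol, since Section 8.1.6 gives levels of 0.05 and 0.005 for pharmacokinetic covariate selection.

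**Conclusion.** The point holds as a defect of method statement with an undefined error rate. Depending on choices the documents leave open, the simulated false-positive rate runs from below 1% to 100%. The main readings are about 7–12% for a median p with nested selection, 34–42% for a naive one-directional t-test over iterations, and 65–100% if selection precedes the folds; some strict rules stay below 2%.

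These figures rest on assumed sample sizes, marker numbers, algorithms and decision rules. They show sensitivity and do not predict what the sponsor will do. It cannot be concluded that the planned analysis is anti-conservative.

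Severity is low. The analysis is optional, exploratory and outside the multiplicity-controlled family, and no primary, secondary or safety conclusion is affected.

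**What to change.** In Section 8.1.7 or the separate biomarker plan:

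1. Replace the significance wording. Report the output as cross-validated predictive performance, name the measure, and state that marker selection, weighting and cut-point choice are redone in each training fold. This is the minimum change and may be enough.
2. Where significance is claimed, add a permutation test. Shuffle outcomes across subjects within treatment group (for example 1,000 times), re-run the whole selection and cross-validation on each shuffled data set, and compare the observed performance with that distribution. State the level and the null being tested; a claim that a marker predicts treatment benefit needs its own null.

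The cost is one or two sentences and computing time, with no new data. The downside is that fewer signatures will be called significant.

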8.2 Determination of Sample Size

The planned total sample size of 600 for this study provides at least 90% power for a 21% difference in ACR20 response rate (assuming a placebo ACR20 response rate of [REDACTED]), as well as at least 90% power for a 22% difference in LDA response rate (based on DAS 28 [CRP] [assuming a placebo LDA response rate of [REDACTED]]), at two sided significance level of 0.025 and accounting for a 10% dropout rate. This sample size will also provide at least 90% power for most of the key secondary endpoints, including change from baseline in DAS28(CRP), change from baseline in HAQ-DI, ACR50 response rate, CR based on DAS28(CRP), and SF-36 PCS, at two-sided significance level of 0.025 and accounting for a 10% dropout rate.

8.3 Randomization Methods

Subjects will be randomly assigned in a 2:2:1:1 ratio to one of the four treatment groups:

- Group 1: Upadacitinib 30 mg QD (N = 200) (Period 1) → Upadacitinib 30 mg QD (Period 2)
- Group 2: Upadacitinib 15 mg QD (N = 200) (Period 1) → Upadacitinib 15 mg QD (Period 2)
- Group 3: Placebo (N = 100) (Period 1) → Upadacitinib 30 mg QD (Period 2)
- Group 4: Placebo (N = 100) (Period 1) → Upadacitinib 15 mg QD (Period 2)

Randomization will be stratified by prior exposure to bDMARD (yes/no) and geographic region.

See Section 5.5.3 for details.

9.0 Ethics

9.1 Independent Ethics Committee (IEC) or Institutional Review Board (IRB)

Good Clinical Practice requires that the clinical protocol, any protocol amendments, the Investigator's Brochure, the informed consent, and all other forms of subject information related to the study (e.g., advertisements used to recruit subjects) and any other necessary documents be reviewed by an IEC/IRB. The IEC/IRB will review the ethical, scientific and medical appropriateness of the study before it is conducted. IEC/IRB approval of the protocol, informed consent, and subject information and/or advertising, as relevant, will be obtained prior to the authorization of drug shipment to a study site.

Any amendments to the protocol will require IEC/IRB approval prior to implementation of any changes made to the study design. The investigator will be required to submit, maintain and archive study essential documents according to International Conference on Harmonization (ICH) GCP.

Any SAEs that meet the reporting criteria, as dictated by local regulations, will be reported to both responsible Ethics Committees and Regulatory Agencies, as required by local regulations. During the conduct of the study, the Investigator should promptly

provide written reports (e.g., ICH Expedited Reports, and any additional reports required by local regulations) to the IEC/IRB of any changes that affect the conduct of the study and/or increase the risk to subjects. Written documentation of the submission to the IEC/IRB should also be provided to AbbVie.

